Patients diagnosed with diabetic foot will have significant changes after hyperbaric treatment such as increased gene expression in the antioxidant response and decreased gene expression in the inflammatory response.

General Objective:

To evaluate gene expression changes in inflammation and oxidative stress in diabetic foot patients treated with hyperbaric oxygen.

Specific objectives:

□ To evaluate the clinical and biochemical characteristics of the included patients according to sex.

□ To evaluate the gene expression of SOD, CAT, GPX, GRd, NLRP3, IL-1b, Casp-1, IL-4, IL-6, IL-10 and IL-13 in the basal state, at 12 and 30 sessions of treatment in the hyperbaric chamber.

Methodology:

Type of study: quasi-experimental, longitudinal, prolective, analytical study.

Characteristics of the population:

Women and men older than 18 years, with Diabetes type 2, residents of the CDMX, with diabetic foot with hyperbaric treatment, attended at the hospital of specialties in diabetes, secretary of health, accepted and signed the informed consent form.

Selection criteria:

Men and women with diabetic foot and hyperbaric treatment. Ages 30-60 years. Signed informed consent form.

Exclusion:

Patients with diabetic foot without presence of dermatologic lesions.

Elimination:

Patients who decided to abandon the protocol. Incomplete data for any variable.

Sample size:

15 patients with diabetic foot.

Operationalization of variables:

Variable	Туре	Measuring unit
Age	Quantitative	Years
Sex	Qualitative	Male/ female
Systemic blood	Quantitative	Milimeters of mercury
pressure		
Waist	Quantitative	Centimeters
Dislipidemias	Qualitative	Positive or negative
Anaemia	Qualitative	Positive or negative
Tabaquism	Qualitative	Positive or negative
Charcot's foot	Qualitative	Positive or negative
Chronic kidney	Qualitative	Positive or negative
disease by CKD-		
EPI I-III		
Insuficiencia	Qualitative	Positive or negative
venosa periférica		
Glucosa en sangre	Quantitative	milligrams/ deciliters
Colesterol	Quantitative	milligrams/ deciliters
Triglicéridos	Quantitative	milligrams/ deciliters
Basal glycosylated	Quantitative	Percentage
hemoglobin basal		
Creatinina	Quantitative	milligrams/ deciliters
Tasa de filtrado	Quantitative	milliliters/ square meter of body surface area
glomerular		
glycosylated	Quantitative	Percentage

hemoglobin at 3		
months		
Wagner's	Qualitative	Wagner
classification for		Grade 0: Absence of ulcers in a high-risk foot.

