- 6. The gRT-PCR technique to determine relative expression, a "master mix" (10 μ L) was prepared in microtubes for the LightCycler nano (Roche Diagnostics), the mix was composed of 100 nM forward oligonucleotides, 100 nM reverse oligonucleotides, 100 nM hydrolysis probe (Human Universal Probe Library, Roche Diagnostics), 2 µL TagMan master (Tag-polymerase), 0. 5 U LightCycler Uracil-DNA glycosylase, and 2 µL of DNAc (500 ng). The mixture was subjected to different temperature changes in the LightCycler Nano Real-Time PCR System (Roche Diagnostics) under the following conditions: initial incubation (denaturation) at 95 °C for 10 minutes, followed by 45 cycles of: denaturation (95 °C for 10 seconds), allylation of oligos to cDNA (60 °C for 30 seconds), and extension (copying) of the cDNA strand (72 °C for 1 minute). The specific sequences used to design the oligonucleotides used in gRT-PCR were ProbeFinder: designed using the online software https://lifescience.roche.com/shop/en/us/overviews/brand/universal-probelibrary.
- Relative RNAm expression of genes was normalized to the relative expression levels of the housekeeping gene (18s). Relative quantification (normalization) of gene expression was determined using the 2-ΔΔΔCT method.

Statistical analysis

In the analysis, qualitative variables are presented in frequencies and percentages, compared with the Chi-square test; quantitative variables according to the Shapiro-Wilk normality test, normally distributed variables are presented in means and standard deviation, compared with Student's t-test, those related with ANOVA test; quantitative variables of free distribution are presented in medians and interquartile ranges, compared with Mann Whitney U-test, those related with Kruskall-Wallis test. Data analysis was carried out with SPSS version 23, Graph Pad Prisma. A value p<0.05 was taken as statistical significance, 95% confidence interval (95%CI).

Ethical aspects:

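### Related, non-normal gene-expression data are assigned to Kruskal-Wallis, an independent-groups test, and no paired or repeated-measures test is named for three measurements in the same 15 patients

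*Combined protocol and SAP*

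**What the plan says.** The combined protocol and SAP describes a "quasi-experimental, longitudinal, prolective, analytical study" with a sample of "15 patients with diabetic foot" and no control group. The second specific objective is to evaluate expression of the listed genes "in the basal state, at 12 and 30 sessions of treatment in the hyperbaric chamber", so each patient contributes three measurements.

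The last step of the Procedure says how expression is expressed: "Relative quantification (normalization) of gene expression was determined using the" delta-delta-CT type method, after normalisation to 18s. The reference sample (calibrator) is not given.

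The Statistical analysis section sorts variables first: "quantitative variables according to the Shapiro-Wilk normality test". Normal variables are "compared with Student's t-test, those related with ANOVA test". Non-normal variables are "compared with Mann Whitney U-test, those related with Kruskall-Wallis test". Qualitative variables go to Chi-square. Nowhere does the document name Friedman's test, the Wilcoxon signed-rank test, a paired t-test, repeated-measures ANOVA or a mixed model.

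**The concern.** Kruskal-Wallis ranks all 45 values (15 patients × 3 times) together and treats them as 45 independent observations. Here they form 15 sets of three, and values from one patient are likely to be correlated. The test then uses the wrong variance for the differences between times, and its p-values do not have their nominal meaning.

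This affects the study's main result. With no control group, the comparison over time within patients is the only evidence on the hypothesis, and with 15 patients the pairing is the main source of precision.

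The non-parametric rule is also likely to be used often, because a fold change computed as a power of 2 is right-skewed and will frequently fail a normality test.

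**Working it through.** There is no power or effect-size figure in the plan to reproduce, so the check is of what the named test does in this design.

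**From the document:** n = 15; 3 time points; significance at p < 0.05.

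**Assumed, because the document does not give them:** normal delta-CT with equal correlation ρ between any two times, ρ = 0 to 0.7; means 0/0/0 under the null and 0/0.4/0.8 SD under the alternative; two possible calibrators. There were 20,000 simulated trials per setting.

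**1. Direction by hand, common calibrator.** Under the null, the variance of a difference between two time means is 2σ²(1 − ρ)/n. An independent-groups test takes it as 2σ²/n. Its statistic is therefore shrunk by roughly (1 − ρ). With 2 degrees of freedom the chi-square tail is exp(−x/2), so a nominal 5% test rejects about 0.05^(1/(1 − ρ)):

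- ρ = 0.2: 0.05^1.25 = 2.4%
- ρ = 0.3: 0.05^1.43 = 1.4%
- ρ = 0.5: 0.05^2 = 0.25%

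**2. Simulation, common calibrator.**

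| ρ | Kruskal-Wallis, null | Kruskal-Wallis, power | Friedman, power |
|---|---|---|---|
| 0 | 4.6% | 43% | 33% |
| 0.2 | 2.6% | 40% | 40% |
| 0.3 | 1.6% | 39% | 45% |
| 0.5 | 0.6% | 36% | 59% |
| 0.7 | 0.1% | 34% | 82% |

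Friedman's null rejection is 4.5 to 4.9% throughout. The two tests have equal power near ρ = 0.2; above that, Kruskal-Wallis loses.

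**3. Simulation, each patient's own baseline as calibrator.** Every baseline value is then the same constant. Kruskal-Wallis rejects a true null 6.6 to 6.9% of the time at every ρ. Its power is 42/49/54/68/88% for ρ = 0/0.2/0.3/0.5/0.7, so none is lost. Friedman's results are identical to those in step 2, because rescaling a patient's three values by one factor leaves their ranks unchanged.

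**4. Baseline against one later time, null rejection (4,000 trials).**

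- Mann-Whitney, common calibrator: 0.2 to 4.6%
- Mann-Whitney, own-baseline calibrator: 11 to 13%
- Wilcoxon signed-rank: 4.1 to 5.3%

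**5. Normal branch, only if one-way ANOVA is meant.** With a common calibrator, null rejection is 4.9/2.6/1.6/0.5/0.1% for the same five values of ρ. Repeated-measures ANOVA with Greenhouse-Geisser correction gives 4.3 to 4.5%.

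**6. How often the non-parametric branch applies.** The figures are the chance that at least one time point of a gene's fold change fails Shapiro-Wilk at n = 15, for ρ = 0.3 to 0.7 and either calibrator. It is 28 to 53% for an assumed delta-CT SD of 0.5 cycles, 68 to 93% for 1.0, and 90 to 100% for 1.5.

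**The case against.** The strongest reply accepts the mismatch but disputes its size and scope.

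- **The 11 to 13% figure.** The plan schedules no contrast between two times and sends related data away from Mann-Whitney, which has a natural use in the comparison by sex. It is fair to call this figure conditional. It remains relevant, because Kruskal-Wallis applied to two time points is essentially the Mann-Whitney test, so following the plan's own rule for a contrast with baseline leads there.
- **The error may be small or conservative.** True in part. With a common calibrator, false positives are not inflated; the harm is lost power. With own-baseline calibration the excess is under 2 percentage points and no power is lost. At ρ = 0 Friedman is the weaker test. The correlation, shift and calibrator are all assumptions.
- **ANOVA for related data most naturally means repeated-measures ANOVA.** Possibly, so that branch is unspecified rather than wrong. If the word *related* is instead a loose translation for more than two groups, the plan has no within-patient test at all.
- **The Shapiro-Wilk percentages depend on assumed SDs and on counting a gene if any one time point fails.** This stands. The any-failure rule alone flags about 12 to 16% of truly normal data. The percentages show only that the branch is not rare.
- **The variable table lists gene expression as qualitative.** Read literally, that sends it to Chi-square, which is not a paired test either. The row needs correcting, but it does not rescue the plan.

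**Conclusion.** The concern holds and must be fixed. The rule for related non-normal data is wrong as written, whatever the correlation or calibrator; the rule for related normal data is incomplete.

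The size of the consequence is conditional. A nominal 5% Kruskal-Wallis test can run anywhere from about 0.1% (common calibrator, ρ = 0.7) to just under 7% (own-baseline calibrator). In the first case power is 34% where Friedman would have 82%. Because the calibrator is not stated, a reader cannot tell whether a reported p-value is too large or too small. Friedman's test and the signed-rank test stay close to 5% in every setting examined. Confidence is high in the mismatch, and lower in any single figure for its effect.

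**What to change.** State the calibrator, list gene expression as quantitative in the variable table, and replace the sentence on related data with wording such as:

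> Gene expression at baseline, 12 and 30 sessions is analysed on the delta-CT (log) scale by repeated-measures ANOVA with Greenhouse-Geisser correction, or by a linear mixed model with a patient random effect; Friedman's test is used if the data are non-normal. Baseline versus 12 and baseline versus 30 sessions are compared by the paired t-test or the Wilcoxon signed-rank test. The same paired tests apply to glycosylated hemoglobin if it is compared over time. Student's t-test and Mann-Whitney are used only for comparisons by sex.

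Choose between the ANOVA and the mixed model in advance; either is acceptable. Fold change can still be shown descriptively. On the log scale, subtracting a patient's own baseline from all three values does not alter the ANOVA, paired or Friedman results, so the calibrator stops mattering for those tests.

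The cost is wording and re-analysis of existing data, with no new samples. The section reports the analysis in the past tense ("Data analysis was carried out with SPSS version 23"), so if it has been run, the change should be reported as post hoc.

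A separate minor point: use Fisher's exact test for 2×2 tables by sex. With 15 patients the smallest expected count cannot exceed 7 × 7/15 = 3.3.

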diabetic feet		Grade 1: Superficial ulcer involving the full
		thickness of the skin but no underlying
		tissues.
		Grade 2: Deep ulcer, penetrating to ligaments
		and muscles but not involving bone or
		abscess formation.
		Grade 3: Deep ulcer with cellulitis or abscess
		formation, almost always with osteomyelitis.
		Grade 4: Localized gangrene.
		Grade 5: Extensive gangrene involving the
		entire foot.
Gene expression	Qualitative	International units
SOD, CAT, GPX,		
GRd, NLRP3, IL-		
1b, Casp-1, IL-4,		
IL-6, IL-10 e IL-13.		

Procedure:

- 1. Patients attended at the diabetic foot clinic in the CDMX were invited to participate. 2.
- 2. An informed consent process was carried out with the patient's signature to agree to participate in the study.
- 3. Questions were asked about their personal pathological and non-pathological history.
- 4. Three tubes of blood samples were taken for determination of blood biometry, urea, creatinine, cholesterol, triglycerides, glycosylated hemoglobin. A 4 ml tube

with EDTA was taken to measure the gene expression of SOD, CAT, GPX, GRd, NLRP3, NLRP3, IL-1b, Casp-1, IL-4, IL-6, IL-10 and IL-13.

- 5. Complementary DNA (cDNA) synthesis was carried out following the instructions of the Transcriptor First Strand cDNA Synthesis kit (Roche Diagnostics), using a mixture of random hexamer primers, nitrogenous bases (A, T, G and C), reaction buffer, RNase inhibitor and Reveso Transcriptase enzyme. The retrotranscription reaction was carried out in a thermocycler (Eppendorf Mastercycler) programmed at an initial temperature of 25°C for 15 minutes, 45°C for 60 minutes and 72°C for 15 minutes.

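### Eleven genes at three time points are judged by one unadjusted p<0.05, with no rule for when the hypothesis is supported, so the chance of false support is left open

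*Combined protocol and SAP*

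**What the plan says.** All references are to the combined protocol and SAP.

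- **Hypothesis:** "Patients diagnosed with diabetic foot will have significant changes after hyperbaric treatment such as increased gene expression in the antioxidant response", followed by a predicted fall in inflammatory expression. The prediction is by class of gene and is introduced as an example.
- **Specific objectives:** "gene expression of SOD, CAT, GPX, GRd, NLRP3, IL-1b, Casp-1, IL-4, IL-6, IL-10 and IL-13 in the basal state, at 12 and 30 sessions", which is 11 genes at three time points.
- **Statistical analysis:** "A value p<0.05 was taken as statistical significance, 95% confidence interval (95%CI". This is the only decision criterion.
- **Tests, same section:** after a Shapiro-Wilk check, normal variables use Student's t-test, "those related with ANOVA test"; the others are "compared with Mann Whitney U-test, those related with Kruskall-Wallis test". No post-hoc procedure is named.
- **Operationalization of variables:** the table row reads "Gene expression Qualitative International units". Under Statistical analysis, "qualitative variables are presented in frequencies and percentages, compared with the Chi-square test".
- **Procedure:** "Relative RNAm expression of genes was normalized to the relative expression levels of the housekeeping gene (18s", so expression is measured as a relative quantity.
- **Sample size:** 15 patients, without a derivation.

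No section names a primary gene, time point or contrast, the number of genes that must change, whether both classes are needed, an adjustment for multiple tests, or an exploratory status. No section assigns each of the 11 genes to a class.

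**The concern.** The hypothesis is worded as a prediction to be confirmed, but the plan gives no way to decide whether it has been. With 11 genes and three time points there are 11 overall tests, or up to 33 pairwise time contrasts. Each can be declared significant at 0.05. One isolated gene could be reported as support for a class-level prediction, and a reader could not tell that from a coherent shift in both classes. The error rate of the claim is set by choices the plan leaves open: which contrast, which direction, how many genes, one class or both, and which test.

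**Working it through.** **Inputs from the documents.** 15 patients, 11 genes, 3 time points, threshold 0.05 per test. The plan states no family-wise error rate and no power, so there is no derived figure to reproduce.

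**Assumptions (not in the documents).** Normal data and two-sided tests. Between-gene correlation is 0, 0.3, 0.5 or 0.7, and within-patient correlation is 0.5 unless stated. For directional rules, 4 antioxidant genes (SOD, CAT, GPX, GRd) and 7 inflammatory. Positive correlation is plausible because every gene is normalised to the same 18s reference. If targets otherwise vary independently, the correlation is V18s/(V18s + Vtarget), which is 0.3, 0.5 or 0.7 when the 18s variance is 0.43, 1 or 2.3 times the target variance.

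**Step 1. Arithmetic for independent genes.**
- Any gene, one overall test each: 1 − 0.95^11 = 0.431.
- Any gene in its predicted direction, one contrast: each test has a 0.025 chance in that direction, so 1 − 0.975^11 = 0.243.
- At least one gene in each class as predicted, one contrast: (1 − 0.975^4) × (1 − 0.975^7) = 0.0963 × 0.1624 = 0.016.

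**Step 2. Null simulation, allowing for correlation** (20,000 trials per setting). Chance of false support:

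| Rule for support, paired test | corr. 0 | 0.3 | 0.5 | 0.7 |
|---|---|---|---|---|
| Any gene, repeated-measures ANOVA | 43% | 38% | 32% | 24% |
| Any gene, any of three paired contrasts | 77% | 71% | 62% | 49% |
| Any gene in predicted direction, baseline to 30 sessions | 24% | 23% | 20% | 16% |
| Both classes as predicted, baseline to 30 sessions | under 2% | 0.3% | under 0.1% | under 0.1% |
| Both classes as predicted, any time pair, mixed freely | 9% | 6% | 5% | 4% |

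**Step 3. Unpaired tests on the repeated samples.** Under the any-gene rule, independent-groups ANOVA or Kruskal-Wallis gives 9–17% at within-patient correlation 0.3, 3–5% at 0.5 and under 1% at 0.7. These tests leave between-patient variation in the error term, so the rate falls as the unknown within-patient correlation rises.

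**Step 4. Effect of adjustment.** On the repeated-measures test, Holm (first step 0.05/11 = 0.00455) or Benjamini-Hochberg brings the chance of any false-positive gene to about 3–5% across the same correlations.

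**Step 5. Power cost, paired t-test, n = 15** (noncentral t). The standardised change detectable with 80% power is 0.78 at 0.05 and 1.11 at 0.00455. At a change of 0.78, power falls from 80% to 40% at the first Holm step. If 3, 5 or 11 genes truly change by 0.78, average per-gene power is about 42%, 43% or 52% with Holm, and 52%, 60% or 74% with false-discovery-rate control.

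**The case against.** The strongest reply is that the large rates belong to the most permissive rule. The hypothesis names two classes with opposite directions. If both must change as predicted on one contrast, false support is under 2% without any adjustment. This stands, and it rules out saying that the plan exceeds 5% on every reading. It does not close the gap, because the plan never adopts that rule: the directions are given as examples, genes are not assigned to classes (the introduction describes NLRP3 as oxidative), and no contrast is chosen.

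A second reply is that the tests named for related data may be conservative. That is also true for their independent-groups versions, as Step 3 shows. But the protection depends on an unknown correlation and comes from ignoring the pairing.

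A third reply is that the study is plainly exploratory, since the Research question only asks what the changes are. The label is nevertheless absent and the Hypothesis reads otherwise.

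Two further inferences are tempting but go too far. The table entry typing gene expression as qualitative, read literally, sends it to Chi-square; beside a Procedure that describes relative quantification, it is more likely a slip than an intended analysis. The introduction lists other markers (TNF-alpha, IL-12, SOD1 and SOD2), and a reader might conclude that the gene family is unknown. The same 11 genes, however, appear in the Specific objectives, the variables table and the Procedure; only the introduction differs.

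**Conclusion.** The point holds as an omission: no primary gene or contrast, rule for support, multiplicity control or exploratory label accompanies a hypothesis of significant change in 11 genes. Confidence in that is high.

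The size is conditional. A reader might infer that the plan carries a false-positive rate of 43% or 77%. The documents do not support that, because those figures need an any-gene, either-direction rule and a paired test, and the plan specifies neither. What can be said is that the choices left open move the chance of false support from under 2% to 77%. The 43% is the top of the range only for one overall test per gene with independent or positively correlated genes.

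All rates rest on the assumed correlations, normal data and the 4/7 split. They suit values with similar spread at each time. If each patient's own baseline is the calibrator for the fold change, which the Procedure does not say, baseline fold changes would have no spread and the model would not apply on that scale.

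**What to change.** 1. **Test.** Treat each gene as quantitative and use a paired method across the three time points (repeated-measures ANOVA, or Friedman where normality fails) in place of Kruskal-Wallis. Correct the type and unit of gene expression in the variables table. This comes first, because the 3–5% after adjustment was computed on a paired test; adjusting p-values from unpaired tests that may already be conservative would only lose power.
2. **Multiplicity.** Report Holm or false-discovery-rate adjusted p-values across the 11 genes of the Specific objectives, beside the unadjusted ones. Mark unadjusted 95% confidence intervals as descriptive. Align the introduction's gene list with the objectives.
3. **Claim.** Keep the hypothesis as written, since rewording it when results may be known would hide what was predicted. Label gene-level results exploratory and state that one unadjusted significant gene does not support the class-level hypothesis.
4. **Only if the data are not yet analysed:** name in advance the contrast, the class and direction of each gene, and whether both classes are required. The Procedure is in the past tense and the Ethical aspects partly in the future, so the documents do not settle whether this option remains.

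The cost is wording, a re-run with paired tests and one column of adjusted p-values; no new data are needed. The claim becomes weaker and power per gene falls as in Step 5. The loss is smaller under false-discovery-rate control, which suits an exploratory report of 15 patients.
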